- Fit Garment to subject in accordance with the sizing chart and instructions provided in the System Training Manual. *Subjects with an under bust chest circumference greater than 52 inches or less than 28 inches are not eligible to be enrolled.*
- Photograph Garment fit (torso only, not subject's head) from both lateral views, the anterior view and the posterior view.
- Set up the WCD including subject ID entry, and synchronization of the WCD internal clock to the current time and time zone. VT/VF detection parameters will remain at default settings. (Refer to the System Training Manual).
- Register the study subject on the CareStation remote monitoring website (Add New Patient) using their study subject ID number.
- Verify Garment fit per System Training Manual using the tablet. Save tablet screen images of the Patient Management, Device Status and WCD Settings screens including the ECG signals.
- Schedule subject to return for follow up (Visit 2)
- Notify the subject that they will receive phone calls on Days 7 +/- 2, 14 +/-2, 21+/- 2, and 28 +/- 2 during which they can ask questions, and during which they will be asked about usage (how long they have been wearing the system), and if they experienced any discomfort or injury. Schedule these weekly phone calls with the subject.

Weekly Phone Calls to Study Subject

On each of Day 7 +/- 2, Day 14 +/- 2, Day 21 +/- 2, and Day 28 +/- 2 the site RC will call the study subject. In preparation for the call, the RC will review daily usage using the CareStation website and will record the usage data in the CRF.

• Record subject questions and responses in the CRF, noting any questions that require additional follow up and when the subject was called again with the answer(s).

Kestra Medical Technologies, Inc. Protocol 3324582_B

- Record subject's explanation for any usage less than 22 hours per day³ since the previous call.
- Ask the subject if they have experienced any discomfort or injury during the previous week. If yes, and the investigator determines that the symptoms are at least possibly related to use of the system, record as an AE in the CRF and gather supporting documentation as appropriate, e.g. description, photograph.

Visit 2: Study Exit Visit

At Visit 2 the following will be performed:

- Photograph garment fit (torso only) from both lateral views, the anterior view and the posterior view.
- Remove the Garment.
- Record WCD System Return (all components).

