- Perform Wearability Assessment after system removal as indicated in the CRF.
- Ask the subject if they have experienced any discomfort or injury since the last phone call. If yes, and the investigator determines that the symptoms are at least possibly related to use of the device, record as an AE in the CRF.
- Have the subject complete the follow up BORG Comfort Scale.
- Have the subject complete the Usability Survey.
- Record subject explanation for usage less than 22 hours per day since the last weekly phone call.
- Obtain ICD summary report via the ICD remote management system or direct interrogation (model number, current programmed parameters, episode detail and any stored electrograms that are available from all new episodes recorded since Visit 1). De-identify and label with subject ID.
- Release the subject from the Visit.

³ Average WCD wear time reported in WEARIT-II Registry Trial (Kutyifa V)

Following the Study Visit:

- Follow up requirements for subjects with ongoing AEs are specified in Section 11.
- If follow-up is needed after the Study Exit visit, it should occur as an unscheduled visit at the Investigator's discretion.

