Adverse events (AEs) as defined below will be monitored continuously during the study from the time the subject is considered enrolled through resolution. Subjects will be instructed to report all AEs during the study, and study personnel will interview the subjects regarding new AEs during each weekly phone call follow up. AEs may be reported by the subject, discovered by Investigator questioning, or detected through physical examination or other means at the study exit visit.

Device Usability Survey

A device Usability Survey will be administered at Visit 2.

Definitions

For the purposes of this study, an **AE** is defined as any untoward medical occurrence in a subject during the study that in the opinion of the investigator is at least possibly-related to use of the ASSURE WCD System.

A serious adverse event (SAE) is defined as any adverse event that:

- Leads to death
- Leads to serious deterioration in the health of a subject that:
 - Results in a life-threatening illness or injury, or
 - Results in a permanent impairment of a body structure or a body function, or
 - Requires in inpatient or prolonged hospitalization \geq 24 hours, or
 - Results in medical or surgical intervention to prevent life-threatening illness or injury or permanent impairment to a body structure or function, or
 - Leads to fetal distress, fetal death or a congenital anomaly or birth defect.

Adverse Device Effect (ADE) is an adverse event related to the use of an investigational medical device.

Anticipated Adverse Device Effects (AADE) are those events related to the use of the device that are reasonably expected to occur as a result of the subject's participation in

the study. The following are AADEs based on results from the series of previous feasibility studies listed in Section 6 and the system engineering hazard analysis:

- Mild to moderate skin irritation
- Muscle Strain
- Emotional discomfort e.g. anxiety, uncomfortable or claustrophobic feelings
- Fall Injury
- Bruising
- Pinched Fingers
- Shoulder discomfort
- Skin Infection (bacterial or yeast)
- ICD System Infection

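### The only worded adverse event questions ask about discomfort or injury, which is narrower than the protocol's AE definition and its own description of the AE interviews

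*Protocol*

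**What the plan says.** Protocol Section 10 offers itself as the detailed account of what is done at each visit. It words the AE enquiry in three places:

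- **Weekly calls (Days 7, 14, 21 and 28):** "Ask the subject if they have experienced any discomfort or injury during the previous week".
- **Visit 2:** "Ask the subject if they have experienced any discomfort or injury since the last phone call".
- **Visit 1 notice:** subjects are told that the calls will cover their usage "and if they experienced any discomfort or injury".

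After both questions, the instruction is to record an AE if the answer is yes and the investigator finds the symptoms at least possibly related.

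Section 11 (Definitions) sets a wider target. An AE is "any untoward medical occurrence in a subject during the study that in the opinion of the investigator is at least possibly-related", the relation meant being with the device. Under Evaluation of Adverse Events, the same section has subjects told to report every AE. Of the weekly contacts it says that "study personnel will interview the subjects regarding new AEs during each weekly phone call follow up".

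The Protocol Summary, Section 9 (Phone Calls) and SAP Section 2.1 describe the weekly calls as a review of potential adverse events. The Protocol Summary and SAP Section 2.1 describe the Visit 2 interview as covering any adverse events since the last call. None of these passages gives a question to ask.

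**The concern.** An event enters the AE data only once it reaches the investigator, who then judges relatedness. A subject cannot apply that judgement, so the sound order is a broad question first and the relatedness filter second. The Section 10 wording narrows the field before the investigator sees anything, and the Visit 1 notice leads subjects to expect questions on the same two categories.

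Safety is a stated secondary objective, and device-related AEs are a secondary endpoint in a study meant to support a premarket application. The Medical Monitor's review for unanticipated adverse device effects works from events that investigators have already judged possibly related. An event that nobody prompts for and the subject does not volunteer never reaches that review and cannot be recovered at analysis. Unexpected effects are the ones a question limited to two expected categories is least likely to draw out.

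**Working it through.** The plan states no figure on this point, so the check sets the passages side by side.

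**1. Contacts carrying the narrow wording.** Four weekly calls plus Visit 2 give 4 + 1 = 5 per subject who completes the study. Section 9 asks that an early withdrawal visit follow the same procedures as the exit visit, so the wording carries over there. This is a count of contacts, not of missed events.

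**2. The question against the protocol's own list.** Section 11 lists nine anticipated adverse device effects.

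- On a plain reading, seven fall within discomfort or injury: skin irritation, muscle strain, emotional discomfort, fall injury, bruising, pinched fingers and shoulder discomfort.
- Two do not fall within it by name: skin infection and ICD system infection. That is 9 − 7 = 2.
- An unanticipated effect that is neither painful nor an injury is also outside it.

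**3. The question against the described interview.** Section 11 requires a weekly interview on new AEs, and the Protocol Summary and SAP Section 2.1 require a Visit 2 interview on any AEs. Section 10 supplies the only wording for those same contacts, and it is narrower. The two can be reconciled only if site staff go beyond the words in Section 10.

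**4. The other routes by which an event could be found.**

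- *Instruction to subjects (Section 11).* It covers all AEs. The only worded notice to subjects, in Section 10, names discomfort and injury.
- *Wearability Assessment (Sections 10 and 11).* It reviews upper-body skin and musculoskeletal findings whether or not the subject complains, and new or worsened related findings become AEs. After baseline it is scheduled once, at exit or early withdrawal, so a skin infection that had already cleared could be missed.
- *Medical history.* Section 11 has it updated whenever the investigator learns of information that would identify AEs. Appendix A marks it again at Visit 2 and early withdrawal, although Section 10 does not list it among the Visit 2 steps. A diagnosed ICD infection could surface here.
- *Investigator questioning and examination (Section 11).* These are named as possible routes. Section 10 lists no general physical examination at Visit 2.
- *BORG scale.* It asks about discomfort again, so it adds nothing for the two infections or a painless effect.

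**5. What is left.** Three kinds of event depend on staff going beyond Section 10 or on the subject volunteering them: ICD system infection, which has no dedicated check; a skin infection resolved before exit; and a painless unanticipated effect.

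**The case against.** The strongest reply is that general AE enquiry is specified for the same contacts. Section 11 requires it weekly, the Protocol Summary and SAP Section 2.1 require it at Visit 2, and the Schedule of Events marks AE collection at every contact. Subjects are also trained and given written instructions that include adverse event reporting. Section 10 tells staff what to ask about and is not a verbatim script; neither a call script nor the case report form is among the documents. Its later reference to symptoms suggests that a general symptom enquiry was intended. The AE definition is itself limited to possibly device-related events, which narrows the gap.

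Much of this stands. A reader might infer that these events are not solicited at all, that an AE can be recorded only after a yes to the narrow question, or that the AE count will be too low. The documents support none of these. The general interviews and the instruction to report all AEs contradict the first. The Wearability Assessment, the medical history update and the other routes in Section 11 contradict the second. Nothing in the documents shows the third. The earlier studies described in Section 6 reported 2 + 6 + 1 + 0 + 9 + 0 + 1 + 8 = 27 AEs, all skin irritation or garment-seam scratches. How those were elicited is not stated, so they neither confirm nor exclude under-ascertainment.

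The reply does not remove the conflict between sections. The general passages supply no question; Section 10 does, and it is narrower than they are. Staff could reasonably take its wording as the way to carry out the interview.

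**Conclusion.** The Section 10 wording, including the Visit 1 notice, is narrower than the AE definition and inconsistent with the AE interviews described elsewhere in the protocol and in the SAP. If sites follow Section 10 literally, the events left over in the working may be under-ascertained. That conclusion assumes literal use of the wording, and the documents do not show how sites will conduct the interviews.

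The effect on the AE summary cannot be sized. The documents give neither the frequency of such events nor the chance that a subject would volunteer one. What can be counted is 2 of 9 anticipated effects outside the wording by name, one of which (skin infection) is partly covered by the exit assessment.

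The consequence is limited. AEs are summarised descriptively with no formal test (SAP Section 4.5), and the false positive alarm analysis is untouched. This is a cheap improvement to a secondary safety endpoint and does not threaten the study's conclusion.

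**What to change.** In Protocol Section 10, change the wording in three places: the weekly call question, the Visit 2 question and the Visit 1 notice. Use one open question that matches the Section 11 definition. For example: any new or worsened medical problem or symptom since the last contact, including discomfort, injury, skin change, infection or emotional effect. Keep the investigator's relatedness step exactly as it is, so that what counts as an AE does not change. Carry the same wording into any call script, subject instructions and case report form prompts.

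The cost is a text edit and a few more unrelated complaints to screen for relatedness. It adds no contacts, procedures or analyses.

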11 STUDY ASSESSMENTS

This section describes the study assessments. For timing of study assessments, see the Schedule of Events (Appendix A).

Demographic Data

Demographic data, such as age, sex, race, and ethnicity will be collected on the CRF

Abbreviated Medical History

An abbreviated medical history as specified in the CRF, including but not limited to cardiac diagnosis and skin allergies will be obtained for each subject at screening and updated any time the Investigator learns of information that might affect the subject's eligibility to continue participation in the study or to identify AEs.

ICD Interrogation and Report Generation

ICD Interrogation at Visit 1 (collect Baseline ICD Documentation via direct interrogation) and at Visit 2 (Obtain ICD summary report via the ICD remote management system or direct interrogation) must be done by qualified site personnel.

BORG Comfort Scale

Subjects will be asked by the research coordinator at baseline and again at the follow up visit to locate and grade the severity of any discomfort they experience on their upper body. This will be recorded on a BORG comfort scale/map as specified in CRFs.

Wearability Assessment

A Wearability Assessment (as specified in the CRF), including a review of skin abnormalities on the upper body and/or musculoskeletal conditions, and measurement of height and weight, will be performed by study personnel. Abnormal findings at Visit 1 will be used to reassess eligibility. If the subject is enrolled, then the findings will be recorded in the CRFs as baseline conditions. The Wearability Assessment will also be performed at Visit 2 after the System has been removed. Height will not be measured or recorded at Visit 2. Abnormal findings that were not present at baseline or have worsened from baseline and are determined by the investigator to be at least possibly related to use of the WCD will be recorded in the CRFs as AEs.

Concomitant Medical Devices and Equipment

Use of allowed concomitant medical devices and durable medical equipment will be recorded in the CRFs (e.g. CPAP, walker, wheelchair).

Clinical Laboratory Tests

Pregnancy testing by urinalysis will be performed for women of child bearing potential to verify eligibility prior to enrollment. Test sticks will be provided by the Sponsor.

Evaluation of Adverse Events

Adverse events (AEs) as defined below will be monitored continuously during the study from the time the subject is considered enrolled through resolution. Subjects will be instructed to report all AEs during the study, and study personnel will interview the subjects regarding new AEs during each weekly phone call follow up. AEs may be reported by the subject, discovered by Investigator questioning, or detected through physical examination or other means at the study exit visit.

Device Usability Survey

A device Usability Survey will be administered at Visit 2.

Definitions

For the purposes of this study, an **AE** is defined as any untoward medical occurrence in a subject during the study that in the opinion of the investigator is at least possibly-related to use of the ASSURE WCD System.

A serious adverse event (SAE) is defined as any adverse event that:

- Leads to death
- Leads to serious deterioration in the health of a subject that:
 - Results in a life-threatening illness or injury, or
 - Results in a permanent impairment of a body structure or a body function, or
 - Requires in inpatient or prolonged hospitalization \geq 24 hours, or
 - Results in medical or surgical intervention to prevent life-threatening illness or injury or permanent impairment to a body structure or function, or
 - Leads to fetal distress, fetal death or a congenital anomaly or birth defect.

Adverse Device Effect (ADE) is an adverse event related to the use of an investigational medical device.

Anticipated Adverse Device Effects (AADE) are those events related to the use of the device that are reasonably expected to occur as a result of the subject's participation in

the study. The following are AADEs based on results from the series of previous feasibility studies listed in Section 6 and the system engineering hazard analysis:

- Mild to moderate skin irritation
- Muscle Strain
- Emotional discomfort e.g. anxiety, uncomfortable or claustrophobic feelings
- Fall Injury
- Bruising
- Pinched Fingers
- Shoulder discomfort
- Skin Infection (bacterial or yeast)
- ICD System Infection

An **Unanticipated Adverse Device Effect (UADE)** is any serious adverse effect on health or safety or any life-threatening problem or death caused by, or associated with the device, if that effect, problem, or death was not previously identified in nature, severity, or degree of incidence in this protocol; or any other unanticipated serious problem associated with the device that relates to the rights, safety, or welfare of subjects.

All AEs will be assessed by the investigator according to:

- Whether the event is serious (SAE);
- The severity of the event (mild, moderate, severe); and
- The relationship of the event to device use (possibly, probably, or definitely related)
 - Possibly Related There is a reasonable possibility that the AE may have been primarily caused by device use. The AE has a reasonable temporal relationship to the use of the device and follows a known or expected response pattern to device, but alternative etiology is equally or more likely compared to the potential relationship to the use of the device.
 - Probably Related There is a reasonable probability that the AE may have been primarily caused by device use. The AE has a reasonable temporal relationship to the use of the device and follows a known or expected response pattern to device. Note: this definition assumes no

alternative etiology is equally or more likely compared to the potential relationship to the use of the device.

 Definitely Related – The AE has a strong causal relationship to device use. The AE follows a strong temporal relationship to the use of the device, follows a known response pattern to the device, and cannot be reasonably explained by known characteristics of the subject's clinical state or other therapies.

Whenever possible, the Investigator should group signs or symptoms that constitute a single diagnosis under a single AE term (e.g. redness and swelling can be combined under skin irritation).

Baseline conditions e.g. mild eczema, and AEs identified at Visit 1 following enrollment will be documented during the Wearability Assessment. Baseline conditions are not considered adverse events unless the condition worsens because of study device use.

Adverse Event Reporting Procedures

SAEs deemed at least possibly related to the use of the ASSURE WCD system will reviewed by the investigator and will be recorded on the CRF. The following information about each AE will be collected: description, severity, onset and resolution dates, seriousness, relationship to study device, action taken, and outcome.

Upon awareness of a SAE, the study site must enter the data into the eCRF within 2-3 business days. If the eCRF is not accessible, the Sponsor or Sponsor representative must be notified of any SAE via [contact]).

UADEs must be reported by the investigator to the approving IRB as soon as possible, but not later than 10 working days after the investigator first learns of the effect.

Reporting UADEs to Regulatory Agencies

The Sponsor is responsible for the ongoing safety evaluation of the device. The Sponsor should promptly notify all concerned Investigators/Institutions and the FDA of findings that could adversely affect the safety of subjects, impact the conduct of the study, or alter IRB approval to continue the study. The Sponsor will report UADEs to the Food and Drug Administration (FDA) and other IRBs within ten days of the Sponsor's learning of them.

Follow-up of Adverse Events

Resolution means the subject has returned to the baseline state of health or the Investigator does not expect any further improvement in the subject's condition or does not expect worsening of the AE.

AEs deemed at least possibly related to the use of the ASSURE WCD system persisting at the time of the subject's study exit will be followed by the investigator until the events are resolved, the subject is lost to follow-up or the adverse events are otherwise explained. If further evaluations are required, the investigator will ensure that relevant additional information is documented in the CRF.

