The Medical Monitor (an independent physician not participating as a clinical investigator in the clinical study) will review and assess in conjunction with the Sponsor all AEs considered by the investigator to be at least possibly related to the use of the ASSURE WCD System to determine if they are reportable to the FDA as Unanticipated Adverse Device Effects (UADEs) per the definition in Section 11. The Medical Monitor will also review all Serious Adverse Events considered by the investigator to be at least possibly related to the use of the ASSURE WCD System to the ASSURE WCD System to verify relatedness and the Serious classification.

Endpoint Review Committee

An independent panel of board-certified electrophysiologists (physicians not participating as clinical investigators in the clinical study) will review all episodes recorded by the ASSURE WCD and/or the subject's ICD in accordance with the *Endpoint Review Committee (ERC) Charter for ASSURE WCD Clinical Evaluation - Detection and Safety Study (ACE-DETECT)* (3334131). These annotations will then be used in the statistical analysis to classify the episodes to calculate the study outcome measures.

Replacements

Subjects who are withdrawn from the study will not be replaced.

Sponsor or Regulatory Agency Termination of the Study

Although the Sponsor intends to complete the study, the right is reserved to discontinue the study at any time for clinical or administrative reasons, or if required by the local regulatory authority.

End of Study

The end of study will be defined as the date of the last visit of the last subject. A summary of the End of Study report will be sent to relevant regulatory authorities and Institutional Review Boards (IRBs) within 6 months of the end of the study.

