6.1 Safety Endpoints

All adverse events that occur during the study will be recorded per the protocol definitions. Per the study protocol, adverse event (AE) is defined as any untoward medical occurrence in a subject during the study that in the opinion of the investigator is at least possibly-related to use of the ASSURE WCD System. For each AE, the Investigator will assess the causality/relationship to the study device (ASSURE™ WCD) and categorize the AE as mild, moderate, or severe, depending on the event's impact on the subject's daily activity level.

Adverse events occurring during the study will be tabulated by type, seriousness, severity, and relationship to the study device. The Medical Monitor assigned to this study will review the adverse events to determine whether any are reportable as UADEs. The Medical Monitor will also review serious adverse events to verify relatedness and the seriousness classification. The Medical Monitor's assessment of seriousness and relatedness, rather than the investigator's assessment, will be used for summarizing and analyzing safety data.

Any deaths or serious device associated AEs will be summarized. AEs leading to subject withdrawal from the study will be listed separately. In cases where the same event is reported more than once per subject, the event will only be counted once in the incidence tables. A listing of all adverse events will be provided.

7. Measurement Scales and Subject Reported Outcomes

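### A non-serious Wearability finding at exit that the investigator calls unrelated is neither reported nor independently checked, and two wording rules in Protocol 11 tighten that filter

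*Protocol*

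**What the plan says.** **The examination.** The Wearability Assessment in Protocol 11 covers upper-body skin, musculoskeletal conditions and body size. Appendix A schedules it at Visit 1, Visit 2 and Early Withdrawal. On the exit examination: "The Wearability Assessment will also be performed at Visit 2 after the System has been removed".

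**How a finding becomes data.** Abnormal exit findings that are new or worse than at baseline, and that "are determined by the investigator to be at least possibly related to use of the WCD will be recorded in the CRFs as AEs", enter the safety data. The AE definition in Protocol 11, repeated in SAP 6.1, makes the investigator's opinion on relatedness part of what an AE is. Appendix A collects only AEs that pass this test, and SAP 4.5 tabulates relatedness as possibly, probably or definitely, with no unrelated row.

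**The grades.** An event graded Possibly Related "follows a known or expected response pattern to device, but alternative etiology is equally or more likely compared to the potential relationship". The two higher grades also refer to a known, or known or expected, pattern.

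**Baseline conditions.** "Baseline conditions are not considered adverse events unless the condition worsens because of study device use" (Protocol 11).

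**The Medical Monitor.** Protocol 9 has the Monitor review "all AEs considered by the investigator to be at least possibly related to the use of the ASSURE WCD System to determine" whether they are reportable as unanticipated adverse device effects (UADEs). SAP 6.1 adds: "The Medical Monitor will also review serious adverse events to verify relatedness and the seriousness classification". SAP 8.5 words the review more broadly, as covering relatedness for adverse events generally, and lists it among the measures against bias.

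**Planned outputs.** The SAP never names the Wearability Assessment. It names the other two exit instruments in SAP 4.3 and plans their analysis in SAP 7: the BORG Comfort Scale, with change from baseline, and the Usability Survey.

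**The concern.** Safety is a secondary objective of a single-arm, open-label study meant to support a premarket application. Skin irritation is the main known harm. In Protocol 6, all nine AEs in the 117-subject prototype study were skin irritation, as were seven of the eight in the 32-subject pilot. The Wearability Assessment is the examination aimed at that harm, and it is done twice on the same subject.

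The plan then passes its exit result through one unblinded judgement. If the investigator decides that a new rash or strain has nothing to do with the device, no table or listing shows it and no independent physician reads it. A reader of the AE tables cannot tell whether few or many exit findings were set aside in this way. The Monitor's review is offered as a bias control, yet it does not reach the judgement where attribution bias would enter.

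**Working it through.** The plan states no figure on this point, so the check is to follow exit findings through the written rules.

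| Finding at exit | Wearability paragraph and AE definition | Other wording in Protocol 11 | Shown in results? | Seen by Monitor? |
|---|---|---|---|---|
| New, non-serious, judged at least possibly related | AE | Consistent if the pattern is known or expected | Yes | Yes |
| New or worse, non-serious, judged unrelated | Not an AE | – | No | No |
| Novel, non-serious, device suspected | AE, in the investigator's opinion | Fails the pattern condition in every grade, read literally | Unclear | Unclear |
| Baseline condition worse, device one of several equally likely causes | AE | Not an AE unless the device caused the worsening | Unclear | Unclear |
| Serious and novel | – | UADE definition applies | Yes, UADEs are summarised | Yes, if an AE |

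**1. Unrelated findings (row 2).** Protocol 9 limits the Monitor to AEs and serious AEs that the investigator already considers related. SAP 6.1 has the Monitor verify relatedness for serious AEs, and SAP 8.5 for AEs in general. The two SAP sections differ, but the answer does not. A finding judged unrelated is not an adverse event under the protocol's definition, so it falls outside both.

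**2. Novel effects (row 3).** An AE must be assigned one of three grades, and each mentions a known, or known or expected, response pattern. An effect nobody has described follows no such pattern. For serious effects the protocol provides for novelty, since a UADE is one "not previously identified in nature, severity, or degree of incidence in this protocol". For non-serious effects there is no matching provision.

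**3. Worsened conditions (row 4).** The Wearability paragraph asks only for possible relatedness. The baseline-conditions sentence asks for causation. Possibly Related admits events for which another cause is as likely or more likely, so the two sentences can give opposite answers for the same subject.

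**4. Other routes to the results.** BORG is not filtered by relatedness and may reflect a painful finding, but it is a subject's discomfort score, and a painless rash need not register. Baseline summaries in Protocol 12 and SAP 8.4 could cover the Visit 1 findings but not those at exit.

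**5. Precision of an all-findings count.** If all 130 subjects had an exit examination and none had a finding left out of the AE data, the exact two-sided 95% upper limit would be 1 − 0.025^(1/130) = 2.8%. Three such subjects (3/130 = 2.3%) would give 0.5% to 6.6%. These limits show what the count could demonstrate. They are not evidence that findings are being left out.

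**The case against.** **The examination is used.** A reader might infer that its data are collected and then ignored. The documents do not support that: the comparison of exit with baseline is itself the AE trigger, and AEs are tabulated and listed. What is missing is any view of findings that stop at the attribution step.

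**The filter is the declared endpoint.** Protocol 8 and SAP 4.3 define the safety endpoint as events at least possibly related to the device, and secondary endpoints are exploratory. This stands, and all-cause AE collection is not what is proposed. The request is for a descriptive summary of one examination already performed.

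**The threshold is low.** Possibly Related admits events with a likelier alternative cause, and the anticipated-effects list covers skin irritation, skin infection, bruising, muscle strain and shoulder discomfort. Most probable findings should therefore be recorded. This is a good reason to rate the point low.

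**The wording is not decisive.** A reader might infer that novel effects are barred outright. That goes too far: the pattern term is undefined, and AE status rests on the investigator's opinion. Likewise, the Wearability paragraph is the specific rule for examination findings and may be taken to govern worsening. Both are conflicts that a site could resolve either way.

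**The Monitor.** It is tempting to say that the Monitor can strike events out but never add them. No text says that an event the Monitor downgrades is deleted. SAP 4.5 tabulates all reported AEs and SAP 6.1 promises a full listing. The supported statement is narrower: the Monitor is never given the findings judged unrelated.

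**Conclusion.** The point holds and is minor. A non-serious exit finding that the investigator judges unrelated appears in no planned output and reaches no independent reviewer. Two sentences in Protocol 11, read literally, set a stricter test than the at-least-possibly-related standard used elsewhere.

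Its size cannot be stated. The documents give no rate at which exit findings are judged unrelated, so an inference that the AE tables undercount harm by some factor has no support. The primary endpoint, sample size and success criterion are unaffected, and serious novel effects have the UADE route. The difference between SAP 6.1 and 8.5 on the Monitor's scope is worth tidying but does not change the conclusion.

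The conclusion rests on the protocol and SAP text alone. The CRF and the Monitor's working procedures were not available and might provide more than the documents say.

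**What to change.** **Protocol 11.** Delete the response-pattern condition from Possibly Related, or state that novel effects qualify. Change the baseline-conditions sentence so that a condition counts when it worsens and is at least possibly related to device use.

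**SAP 6.1.** For Safety-set subjects with an exit examination, at Visit 2 or Early Withdrawal, add a descriptive count and listing of new or worsened Wearability findings regardless of attribution, showing how many were not recorded as AEs. Give the listing to the Medical Monitor before database lock. Show any finding the Monitor judges at least possibly related as a flagged line beside the investigator-reported AEs, leaving the investigator's record as it is.

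**Cost.** Two wording edits, one table, one listing and one read by the Monitor. Exit findings are probably captured whatever their cause. Protocol 10 has the exit assessment done as the CRF indicates, and Protocol 11 singles out one item to omit: "Height will not be measured or recorded at Visit 2". That is an inference. If the CRF does not hold unrelated findings, one field must be added.

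**Limits.** Without a comparator the count cannot separate background findings from device effects. The Monitor will not have examined the subject. Irritation that resolved before exit will not appear.
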